4.7.2 Baseline

As defined in [Section 2.8.2](#), the last available assessment before or on the date of start of study drug is defined as “baseline” value or “baseline” assessment.

Laboratory data

If both central and local laboratory assessments were performed on the same date and corresponding to the baseline assessment date, then the central laboratory assessment will be used for the calculation of baseline.

If labs with duplicate laboratory measurements taken at the last assessment date on or before the start date of study treatment from the same sources (both from local or central), then the rule described below will be applied for the calculation of baseline.

- For gradable labs, the value of lower CTCAE grade will be considered as the baseline value. If several records have the same absolute grade, but in different directions, 2 baselines should be created, the record with grade below 0 should be the baseline of the 'Hypo' parameter, and the other record should be the baseline for the 'Hyper' parameters.
- For non-gradable labs:
 - If both within normal range: take average value
 - If one within normal range and the other outside: take the one within normal range
 - If both outside normal range: take the one closest to the normal range

ECGs

Baseline for ECG measurement is the average of the pre-dose replicate measurements on the baseline day. Unscheduled assessments will not be included in the calculation of the average. Study day 1 scheduled pre-dose ECGs will be considered to have been obtained prior to study drug administration if dosing time or ECG time is missing.

If a scheduled pre-dose measurement actually occurred post-dose, then the corresponding measurement will be treated and analyzed similar to an unscheduled post-dose measurement. For unscheduled assessments on study day 1, the assessment is classified as post-baseline.

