**Table 7-6 ECG collection plan for remaining patients, including patients in Cohort 6 and Cohort 7**

Cycle	Day	Time	ECG Type	Number of ECGs
Screening		Anytime	12 Lead	3
1	1	Pre-dose	12 Lead	3
1	15	Post-dose 2 h (within 15 min prior to PK)	12 Lead	3
3	1	Pre-dose	12 Lead	3
EOT		Anytime	12 Lead	3
Unscheduled ECG		Anytime if clinically indicated	12 Lead	3

Baseline is defined as the pre-dose assessment on Cycle 1 Day 1 before study drug administration.

All ECG assessments will be performed in the supine position. Detailed instructions regarding the ECG collection will be provided to the investigators in a separate manual prior to the start of the study. INC280 pharmacokinetic evaluation will be conducted in parallel to cardiac evaluations (see [Section 7.2.3](#)). All ECGs should be performed within 15 minutes prior to the collection of PK sample. The triplicate ECGs should be taken approximately 2-4 minutes apart. An ECG may be repeated at the discretion of the investigator at any time during the study and as clinically indicated.

All ECGs recorded for each time point will be transmitted electronically to a central laboratory and will be centrally reviewed by an independent reviewer. Any original ECG not transmitted electronically to the central laboratory should be forwarded for central review. Review of all ECGs from a particular patient should be performed by a single reader. The ECG lead for interval duration measurements should be pre-specified. Baseline and all subsequent ECGs should be based on the same lead.

Interpretation of the tracing must be made by a qualified physician. Each ECG tracing should be labeled with the study number, patient initials (where regulations permit), patient number, ECG nominal day and time, ECG actual date and time (using a 24-hour clock, record up to second), ECG replicate number, measured variables (QT, RR, PR, QRS), derived variables

(QTcB, QTcF, and HR), ECG lead date, and kept in the source documents at the study site. Clinically significant abnormalities present when the patient signed informed consent should be reported on the Medical History eCRF page. Clinically significant findings must be discussed with Novartis prior to enrolling the patient in the study. New or worsened clinically significant findings occurring after informed consent must be recorded on the Adverse Events eCRF page.

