2.8.2 Safety

All safety analyses will be performed based on the Safety Set by cohort and also for all patients. Safety will also be presented combining the MET mutant cohorts and amplified cohorts as defined in [Section 2.2](#).

Baseline

Baseline is the result of an investigation describing the “true” uninfluenced state of the patient. The last available assessment before or on the start date of study drug is defined as “baseline” value or “baseline” assessment. If an assessment is planned to be performed prior to the first dose of study drug in the protocol and the assessment is performed on the same day as the first administration of study drug, it will be assumed that it was performed prior to study drug administration, if assessment time point is not collected or is missing. If assessment time points are collected, the observed time point will be used to determine pre-dose on study day 1 for baseline calculation. Unscheduled assessments will be used in the determination of baseline. See [Section 4.7.2](#) for further details on derivation of baseline for laboratory data and ECGs.

Patients who start treatment and discontinue from the study on the same day may have 2 different sets of data collected on study day 1, one being reported to the cycle 1 day 1 visit, the other reported to the end of treatment (EOT) visit. Data reported at the EOT visit are not eligible for baseline selection.

Grouping for the analyses

The overall observation period will be divided into three mutually exclusive segments:

- Pre-treatment period: from day of patient’s informed consent to the day before first dose of study drug
- On-treatment period:
 - For discontinued patients, from day of first dose of study drug to 30 days after last dose of study drug
 - For ongoing patients, from day of first dose of study drug to the data cut-off date
- Post-treatment period: starting at day 31 after last dose of study drug

The safety summary tables will include only assessments collected no later than 30 days after study drug discontinuation and assessments prior to the data cut-off date for on-going patients, unless otherwise specified.

For select items, shift tables or change from baseline summaries generated for laboratory, ECG, vital signs and change score generation may use data from pre-treatment period for baseline calculations.

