4.7.1 Multiple assessments within post-baseline visits

For all analyses regarding abnormal assessments or analyses based on worst or best post-baseline value (laboratory, ECGs, vital signs, ECOG performance status), all post-baseline values will be included (scheduled, unscheduled, repeat). All unscheduled and repeat measurements will be included in listings.

Laboratory Data

For laboratory data, assessments can be collected from both local and central laboratory on the same date. For shift tables using CTC grades to compare baseline to the worst post-baseline value, the assessment with worst post-baseline value is used for analyses irrespective of the source. For LFT summaries, where concurrent measurements are used in the calculation of number and percentage of patients with worst post-baseline values, the assessment with worst post-baseline value is used (since worst values are based on the largest ratio of lab value to its ULN for each patient) although the worst values for the different parameters may be coming from different laboratories.

ECGs

For all patients, 3 ECGs are targeted to be measured at the protocol-defined (nominal) time-points. If a patient has more than one measurement at a nominal scheduled time point, the average of all available measurements associated with the nominal time point will be used for the analyses. For unscheduled visits, measurements taken within 15 min interval will also be averaged and used for analysis.

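### SAP 4.7.2 classes every unscheduled Study Day 1 ECG as post-baseline, even one documented before the first dose, so a drug-free QTc value can enter the post-baseline ECG tables

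*SAP*

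**What the plan says.** SAP 2.8.2 (Safety, Baseline) sets the general rule for safety data. It states that "Unscheduled assessments will be used in the determination of baseline" and that, where times are collected, "the observed time point will be used to determine pre-dose on study day 1 for baseline calculation". It then refers to SAP 4.7.2 for the details on laboratory data and ECGs.

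SAP 4.7.2 opens by citing the 2.8.2 definition. For ECGs it takes baseline as the mean of the pre-dose replicates on the baseline day and adds three rules:

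- On the baseline mean: "Unscheduled assessments will not be included in the calculation of the average".
- A tracing planned as pre-dose but in fact recorded after dosing leaves baseline and is handled like any unscheduled tracing taken after the dose.
- On unscheduled tracings that day: "For unscheduled assessments on study day 1, the assessment is classified as post-baseline".

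SAP 4.7.1 says that for abnormality analyses and for worst- or best-value analyses, "all post-baseline values will be included (scheduled, unscheduled, repeat"). The ECG part of SAP 2.8.2 uses post-baseline values for the notable-value counts and for the shift table from baseline to worst value for QT, QTcF and QTcB.

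In the protocol, section 7.2.2.6.1 says: "Baseline is defined as the pre-dose assessment on Cycle 1 Day 1 before study drug administration". The same section lets the investigator repeat an ECG at any time.

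**The concern.** On Study Day 1 a patient is drug-free until the first tablet and exposed afterwards. Only the time of the ECG relative to the dose separates the two states. The last ECG sentence of SAP 4.7.2 ignores that time for unscheduled tracings and treats all of them as post-baseline.

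Two things could go wrong. First, a pre-dose repeat with a higher QTc could be reported as a new notable value or as a patient's worst post-baseline value before any INC280 was taken. Second, if the scheduled pre-dose replicates cannot be used, a valid unscheduled pre-dose ECG could not replace them. The patient's reference would then be an older ECG or none, while the real pre-dose value would sit in the post-baseline data. Most patients have only three scheduled post-baseline ECG time points (Cycle 1 Day 15, Cycle 3 Day 1 and end of treatment, protocol Table 7-6), so one misplaced value can set a patient's worst value.

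**Working it through.** There is no planned figure to reproduce. The check follows one ECG through the rules.

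**Inputs**

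- Class of an unscheduled Day 1 ECG: post-baseline, with no time condition (SAP 4.7.2).
- Entry to the baseline mean: unscheduled ECGs are excluded (SAP 4.7.2).
- Start of the on-treatment period: the day of first dose, not the time (SAP 2.8.2, grouping for the analyses).
- ECG time: each tracing carries its actual date and time, to the second (protocol 7.2.2.6.1).
- Dosing time: entered in the eCRF on PK days (protocol 6.1.1). Cycle 1 Day 1 is a PK day in both sampling schedules (protocol Tables 7-7 and 7-8).

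**Case 1: scheduled pre-dose triplicate available** (assumed values)

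1. Scheduled pre-dose mean QTcF = 445 ms; unscheduled pre-dose ECG = 455 ms.
2. Under 4.7.2, baseline stays at 445 ms and 455 ms is post-baseline.
3. 455 ms lies above 450 and not above 480, so it can count as a new value in that category. The on-treatment filter does not remove it, because that period begins with the calendar day.
4. The change is 455 − 445 = 10 ms, below the 30 ms cut-off, so no increase-from-baseline category is met.
5. Under the observed-time rule of 2.8.2, the 455 ms tracing is pre-dose and is not counted as post-baseline.

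**Case 2: no evaluable scheduled pre-dose replicate**

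Let S be the earlier ECG (for example screening), P the unscheduled pre-dose Day 1 ECG, and X any later value.

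1. Under 4.7.2, P cannot enter baseline, so baseline = S, or is missing if there is no S.
2. The reported change is X − S. With P as baseline it would be X − P.
3. The difference is (X − S) − (X − P) = P − S. The change is overstated when P is above S and understated when P is below S.
4. P itself is also counted as post-baseline, giving a drug-free change of P − S.

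**Asymmetry inside 4.7.2.** Actual timing moves a scheduled pre-dose ECG out of baseline if it was really taken after the dose. The reverse correction, for an unscheduled ECG really taken before the dose, is not made.

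**Scale of one patient.** SAP 2.2 gives 373 patients in total: 1/373 = 0.27 percentage points.

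**The case against.** The strongest reply is that there is no live contradiction. SAP 2.8.2 gives a general rule and sends the reader to 4.7.2 for ECGs, so the specific rule governs. That reading is right, but it confirms that the rule would be programmed as written. It does not explain why a documented pre-dose ECG should be post-baseline, and 4.7.2 presents itself as applying the 2.8.2 definition.

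The protocol sentence is weaker support. It can fairly be read as meaning the scheduled triplicate in Tables 7-5 and 7-6, so the point does not depend on it.

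Several limits stand:

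- Case 1 can only add QTc findings, and all ECGs are listed, so a misplaced tracing can be seen on review. Change-from-baseline summaries at nominal times are little affected.
- Case 2 is narrow. Nothing requires all three replicates, so the whole scheduled set must be unusable or post-dose. The replacement must also be recorded as unscheduled. SAP 4.7.1 averages all measurements attached to a nominal time point, so a repeat logged to the pre-dose time may not be unscheduled at all. A screening fallback is still drug-free.

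A reader might infer more than the documents support:

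- *Counts of adverse events of special interest are distorted.* QTc prolongation is on that list, but SAP 2.8.2 builds these groupings from MedDRA terms for reported events. Reclassifying an ECG measurement changes none of them.
- *The protocol's preliminary 4/110 (3.6%) with a 30 to 60 ms increase would become 5/110 (4.5%).* That needs a pre-dose repeat more than 30 ms above the same-day mean, and no such case is documented. The 110 patients come from an earlier preliminary analysis, not from the 373 covered here.
- *Pre-dose repeats happen mostly when a tracing is borderline or unusable.* The documents do not say so.

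**Conclusion.** The point holds as a defect in the stated rule. Under SAP 4.7.2 a documented pre-dose unscheduled ECG on Study Day 1 can be counted in the notable-value tables and in the worst-value QT, QTcF and QTcB shift table. Less often, it is also barred from serving as the baseline it should supply.

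The size is unknown and may be zero, because the number of such ECGs is not documented. The first effect errs towards over-counting. The second can bias a patient's change from baseline either way. A reader might conclude that true baselines are generally lost; that happens only when no scheduled pre-dose replicate is evaluable. No efficacy result depends on the rule. The conclusion assumes that ECG and dosing times are in the analysis data, which SAP 4.7.2 itself presupposes when it says what to do if either is missing.

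**What to change.** Replace the last ECG sentence of SAP 4.7.2 with wording such as:

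> Unscheduled ECGs on study day 1 are classified as pre-dose or post-dose from the recorded ECG time and dosing time. Those documented as pre-dose are never post-baseline. If no evaluable scheduled pre-dose replicate exists, the average of the unscheduled pre-dose ECGs is the baseline. An unscheduled ECG is post-baseline by default only if either time is missing.

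Limit the neighbouring exclusion, "Unscheduled assessments will not be included in the calculation of the average", to patients who have scheduled pre-dose replicates available. Otherwise it conflicts with the new text.

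The cost is two short edits and one programming condition on times the protocol already requires. There is one small downside. SAP 2.1 lists four earlier data cut-offs; if those reports used the present convention, which the documents do not show, QTc counts may differ slightly from them. A footnote on the affected tables would cover this.

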4.7.3 Laboratory Parameters

This section provides further detail on the analysis of laboratory parameters that will be listed and summarized as described in [Section 2.8.2](#).

Hematology

Hematologic tests include: Hemoglobin, platelets, white blood cells (WBC), red blood cells (RBC), differential (basophils, eosinophils, lymphocytes, monocytes, neutrophils (% or absolute)

The following rules will be applied to derive the WBC differential counts when only percentages are available (this is mainly for neutrophils and lymphocytes, because CTC grading is based on the absolute counts).

The method to convert the value is straightforward: for each patient, the original lab value (%) is divided by 100 and multiplied by WBC count e.g. for neutrophils (NEU):

$$\text{NEU count} = (\text{WBC count}) * (\text{NEU\%value}/100)$$

In order to derive the corresponding absolute normal range, the rule to be applied depends on the availability of the % range and the absolute range for the differential:

- If % absolute range NOT missing (% range is or isn't missing), then use the absolute range provided by the site
- If % range NOT missing and absolute range missing, then the % normal limits (i.e LLN and ULN) are divided by 100 and multiplied by the corresponding normal limits of WBC count, e.g. for neutrophils NEU):

$$\text{LLN for NEU count} = (\text{LLN for WBC count}) * (\text{LLN for NEU\%value}/100)$$

$$\text{ULN for NEU count} = (\text{ULN for WBC count}) * (\text{ULN for NEU\%value}/100)$$

Biochemistry

The following calculation will be applied for corrected calcium in SI unit (if not available in the Lab database):

Corrected calcium (mmol/L)=measured total Ca (mmol/L)+0.02 (40-serum albumin[g/L]), where 40 represents the average albumin level in g/L.

Time windows will be defined for trends of labs over time.

Table 4-6 Time windows for Labs

Time Window	Planned Visit Timing	Time Window Definition
Baseline	On or before Study Day 1	≤ Study Day 1
Cycle 1 Day 15 (Week 3)	Study Day 15	Study Days 2 – 18
Cycle 2 Day 1 (Week 4)	Study Day 22	Study Days 19 – 32
Cycle 3 Day 1 (Week 7)	Study Day 43	Study Days 33 – 53
Cycle 4 Day 1 (Week 10)	Study Day 64	Study Days 54 – 74
Cycle 5 Day 1 (Week 13)	Study Day 85	Study Days 75 – 95
Cycle 6 Day 1 (Week 16)	Study Day 106	Study Days 96 – 116
Cycle 7 Day 1 (Week 19)	Study Day 127	Study Days 117 – 137
Every 6 weeks thereafter	Scheduled visit day (+ 21 days from previous cycle)	Scheduled visit day ± 10 days centered around the planned assessment

Study Day 1 = the first day of dosing

4.7.4 Time to first occurrence of event and duration

This section provides additional details to those included in [Section 2.8.2](#). For each case, the start date and end date for the duration of the 1st occurrence are in bold.

Case 1a: First event resolved with a single event - Outcome = recovered/resolved

Patient ID	Preferred term	Start date	End date	Grade	Outcome
0001	INCREASED LIPASE	2016-05-31	2016-06-02	3	RECOVERED/RESOLVED

Case 1b: First event resolved with multiple events with the same start date - Outcome = recovered/ resolved

Patient ID	Preferred term	Start date	End date	Grade	Outcome
0002	INCREASED AMYLASE	2018-10-01	2018-10-29	3	RECOVERED/RESOLVED
	INCREASED LIPASE	2018-10-01	2018-11-20	3	RECOVERED/RESOLVED

Case 2a: The first event improved with a single event - Outcome = recovering/resolving

Patient ID	Preferred term	Start date	End date	Grade	Outcome
0003	ILD	2017-08-30	2017-09-20	3	RECOVERING/RESOLVING
	ILD	2017-09-21	2017-10-06	2	NOT RECOVERED/NOT RESOLVED
	ILD	2017-10-07		3	NOT RECOVERED/NOT RESOLVED

Case 2b: The first event improved with multiple events with the same start date - Outcome =recovering/resolving

Patient ID	Preferred term	Start date	End date	Grade	Outcome
0004	AST INCREASED	2017-11-30	2017-12-06	3	RECOVERING/RESOLVING
	HYPOALBUMINEMIA	2017-11-30	2017-12-06	2	RECOVERING/RESOLVING
	ALT INCREASED	2017-11-30	2017-12-13	3	RECOVERING/RESOLVING
	GGT INCREASED	2017-11-30	2018-01-12	2	RECOVERED/RESOLVED
	ALP INCREASED	2017-12-06	2017-12-13	1	RECOVERED/RESOLVED
	AST INCREASED	2017-12-06	2017-12-13	2	RECOVERING/RESOLVING
	ALT INCREASED	2017-12-13	2017-12-20	2	RECOVERING/RESOLVING
	AST INCREASED	2017-12-13	2017-12-20	1	RECOVERED/RESOLVED
	ALT INCREASED	2017-12-20	2018-01-12	1	NOT RECOVERED/NOT RESOLVED
	AST INCREASED	2018-01-12	2018-01-22	3	RECOVERING/RESOLVING
	ALT INCREASED	2018-01-12	2018-01-25	4	RECOVERING/RESOLVING

Case 2c: The first event improved (Gr 4, Gr 3 and Gr <3) - Outcome =recovering/resolving

Patient ID	Preferred term	Start date	End date	Grade	Outcome
0005	HEPATIC DYSFUNCTION	2017-01-06	2017-01-11	4	RECOVERING/RESOLVING
	HEPATIC DYSFUNCTION	2017-01-12	2017-01-18	3	RECOVERING/RESOLVING
	HEPATIC DYSFUNCTION	2017-01-19	2017-02-06	1	RECOVERED/RESOLVED

Case 3a: The first event worsened and then improved (Gr 3, Gr 4 and Gr <3) - Outcome =not recovered/not resolved and then recovering/resolving

Patient ID	Preferred term	Start date	End date	Grade	Outcome
0006	AMYLASE INCREASE	2017-07-13	2017-07-18	2	RECOVERING/RESOLVING
	AMYLASE INCREASE	2017-07-19	2017-08-29	1	NOT RECOVERED/NOT RESOLVED
	AMYLASE INCREASE	2017-08-30	2017-09-05	3	NOT RECOVERED/NOT RESOLVED
	AMYLASE INCREASE	2017-09-06	2017-09-10	4	RECOVERING/RESOLVING
	AMYLASE INCREASE	2017-09-11	2017-09-21	3	RECOVERING/RESOLVING
	AMYLASE INCREASE	2017-09-22		1	NOT RECOVERED/NOT RESOLVED

Case 3b: The first event worsened with multiple events and then improved (Gr 3, Gr 4 and Gr <3) - Outcome =not recovered/not resolved and then recovering/resolving

Patient ID	Preferred term	Start date	End date	Grade	Outcome
0007	AMYLASE INCREASED	2017-09-12	2017-10-05	3	NOT RECOVERED/NOT RESOLVED
	AMYLASE INCREASED	2017-10-06	2017-10-20	3	RECOVERING/RESOLVING
	LIPASE INCREASED	2017-10-06	2017-10-20	1	RECOVERED/RESOLVED
	AMYLASE INCREASED	2017-10-20	2017-10-26	1	NOT RECOVERED/NOT RESOLVED
	LIPASE INCREASED	2017-10-26	2017-11-03	3	RECOVERED/RESOLVED
	AMYLASE INCREASED	2017-10-27	2017-11-20	3	RECOVERING/RESOLVING
	AMYLASE INCREASED	2017-11-20	2017-12-11	2	RECOVERED/RESOLVED
	AMYLASE INCREASED	2017-12-11		1	NOT RECOVERED/NOT RESOLVED

Case 4: The first event worsened and then resolved - Outcome =not recovered/not resolved and then recovered/resolved

Patient ID	Preferred term	Start date	End date	Grade	Outcome
0008	HEPATOTOXICITY	2015-11-17	2015-11-22	3	NOT RECOVERED/NOT RESOLVED
	HEPATOTOXICITY	2015-11-23	2015-12-02	4	RECOVERING/RESOLVING

	HEPATOXICITY	2015-12-03	2016-01-19	3	RECOVERED/RESOLVED WITH SEQUELAE
	GGT INCREASED	2016-01-05		2	NOT RECOVERED/NOT RESOLVED

4.7.5 Handling of AEs missing grade

- Missing grade will be included under 'All grades' column for AE tables displaying 'Grade 3/4' and 'All grades'.
- Missing grade will be counted twice for AE tables by maximum grade (displaying Total, Grade 1–4 and Missing).

4.8 Imputation rules

4.8.1 Study drug

The following rules should be used for the imputation of the dose end date for a given study treatment component:

Scenario 1

If the dose end date is completely missing and there is no end of treatment (EOT) page and no death date, the patient is considered as on-going.

The patient should be treated as on-going and the cut-off date should be used as the last dosing date.

Scenario 2

If the dose end date is completely or partially missing and the EOT page is available:

- Case 1: The dose end date is completely missing and the EOT completion date is complete, then this latter date should be used.
- Case 2: Only year (YYYY) of the dose end date is available and YYYY < the year of EOT date, then use 31DECYYYY
- Case 3: Only year (YYYY) of the dose end date is available and YYYY = the year of EOT date, then use EOT date
- Case 4: Both year (YYYY) and month (MMM) are available for dose end date and YYYY = the year of EOT date and MMM < the month of EOT date, then use last day of the Month (MMM)
- Case 5: Both year (YYYY) and month (MMM) are available for dose end date and YYYY = the year of EOT date and MMM = the month of EOT date, then use EOT date

All other cases should be considered as a data issue and the statistician should contact the data manager of the study.

After imputation, compare the imputed date with start date of treatment.

- If the imputed date is < start date of treatment, then use the treatment start date
- Otherwise, use the imputed date

Patients with missing start dates are to be considered missing for all study treatment component related calculations and no imputation will be made. If start date is missing then end-date should not be imputed.

